The main risk associated with the use of OACs is the occurrence of serious bleeding events requiring careful use and regular treatment reevaluation. Among patients with AF, some populations have this risk of bleeding potentially increased, especially the elderly and frail (8,9), or those having dementia (10). The risk is also increased in patients with coronary arterial disease (CAD) due to antithrombotic therapy with dual antiplatelet and OAC (4). In case of contraindication to oral anticoagulation, in particular because of major risk of bleeding, a left atrial appendage (LAA) occlusion may be considered to prevent the risk of thromboembolism (11,12).

In France, two previous studies published by Santé Publique France described the annual rate of adult patients newly treated with OAC for AF using data from the National Health Data System (SNDS), of which the most recent published in 2021 estimates in 2018 a standardized rate of 410/100,000 inhabitants (6,7). To our knowledge, no such recent French epidemiological data specific to AF unexposed to OAC is available.

The use of OACs and the associated risks were evaluated in the NACORA study conducted in 2014 by the National Health Insurance (CNAM) in collaboration with the National Agency for Medicines and Health Products Safety (ANSM), using data from the SNDS. This study assessed in France, the hemorrhagic and thromboembolic risks in AF patients exposed to VKA and DOAC (rivaroxaban and dabigatran only), over a short exposure periods of 6 months and a study period from 2011 to 2012 (13,14).

Pfizer and BMS laboratories conducted the NAXOS study, following the methodology of the NACORA study, published in 2020, for the reassessment of the reimbursement of apixaban on the data from the SNDS. The NAXOS study compared the 1-year risk of occurrence of stroke and systemic embolism (SE) and major bleeding in patients initiating OACs (apixaban, rivaroxaban, dabigatran, and VKAs) between 2014 and 2016 with AF (15).

By contrast, there is no such data in AF patients unexposed to OAC in France.

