8.1 Primary Objective

1. To estimate the incidence rate of stroke (ischemic or hemorrhagic), major bleeding and death in both non-valvular AF patients exposed to OAC (VKA or DOAC) and unexposed to OAC, overall and in the following subgroups of interest:
 - Elderly (≥ 80 years old)
 - Patients with CAD
 - Frail patients
 - Patients reported with active cancer
 - Patients reported with previous stroke

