9.2.3.4 Sub-Populations

Five subpopulations will be considered in order to meet the objectives of the study:

- Elderly NVAF patients stratified on age-group (≥ 80 years old);
- NVAF patients having a history of coronary arterial disease (CAD);
- NVAF frail patients;
- NVAF patients having an active cancer;
- NVAF patients reported with previous stroke.

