Age ≥ 80 years old	
Binary variable (<80 years old / ≥ 80 years old)
 
Derived based on the date of birth attributed to the patient after cleaning the data extraction
 
Equals to:
 
 13. “<80 years old” if the absolute difference between the year of index date and the year of birth is strictly lower than 80 years old 14. “≥ 80 years old” if the absolute difference between the year of index date and the year of birth is upper than 80 years old 
See also Data Management Plan in section Error! Reference source not found.

History of coronary arterial disease (CAD)	
Binary variable (Yes / No)
 
Equals to “Yes” if the patient meets any criterion below on or in the 2 years prior to the index date:
 
 15. Is hospitalized with any diagnosis (i.e., main, related or associated diagnosis) of coronary arterial disease 
ICD-10 codes: I21.x, I22.x, I24.x, I25.x
 
OR
 
 – Is covered by the LTD status for coronary arterial disease at least one day 
ICD-10 codes: I21.x, I22.x, I24.x, I25.x
 
Equals to “No” in other cases

Claims-based Frailty Index (CFI) (for frail patients’ derivation)	
Continuous variable (between 0 and 1)
 
Claims-based frailty index (CFI) estimates a deficit-accumulation frailty index from a clinical assessment using International Classification of Diseases (ICD) diagnosis codes, Current Procedural Terminology (CPT) codes, and Healthcare Common Procedure Coding System (HCPCS) codes in the prior 2 years in administrative claims data.
 
See more details on calculation of CFI in Appendix 22

Frail patients	
Binary variable (Yes / No)
 
Equals to “Yes” if the Claims based Frailty Index (CFI) is upper or equal to 0.20
 
See Table I variable Claims based Frailty Index (CFI)

Active cancer	Binary variable (Yes / No)

Equals to “Yes” if the patient meets any criterion below in the 2 years before index date:
 
16. Is hospitalized with any discharge diagnosis (i.e., main, related or associated diagnosis) of active cancer
 
ICD-10 codes: C00.x to C80.x, D00.x to D09.x, D37.x to D48.x, Z51.0, Z51.1
 
OR
 
 – Is covered by the LTD status for active cancer at least one day 
ICD-10 codes: C00.x to C80.x, D00.x to D09.x, D37.x to D48.x, Z51.0, Z51.1
 
Equals to “No” in other cases
	

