Solid metastatic tumor (for ACCI derivation)	
Binary variable (Yes / No)
 
Equals to “Yes” if the patient meets any criterion below on or in the 2 years prior to the index date:
 
 – Is hospitalized at least once with any discharge diagnosis (i.e., main, related or associated diagnosis) of metastatic tumor 
ICD-10 codes : C77.x, C78.x, C79.x, C80
 
OR
 
 – Is covered by the LTD status for metastatic tumor at least one day 
ICD-10 codes : C77.x, C78.x, C79.x, C80
 
Equals to “No” in other cases

Age adjusted Charlson Cormordity Index (ACCI) adapted to the SNDS data	
Continuous variable (point)
 
Derived based on (20,23)
 
Equals to the sum of:
 
 ○ 0 point if the variable History of diabetes equals to “Yes” ○ 0 point if the variable History of diabetes with complications equals to “Yes” ○ 0 point if the variable History of myocardial infarction equals to “Yes” ○ 2 points if the variable Heart failure equals to “Yes” ○ 1 point if the variable Peripheral vascular disease equals to “Yes” ○ 1 point if the variable Cerebrovascular disease equals to “Yes” ○ 1 point if the variable Moderate-to-severe renal disease equals to “Yes” ○ 2 points if the variable Mild liver disease equals to “Yes” ○ 3 points if the variable Moderate-to-severe liver disease equals to “Yes” ○ 1 point if the variable Chronic pulmonary disease equals to “Yes” ○ 2 points if the variable Dementia equals to “Yes”

	
 ○ 0 point if the variable Connective tissue disease equals to "Yes" ○ 0 point if the variable Ulcer disease equals to "Yes" ○ 2 points if the variable Hemiplegia equals to "Yes" ○ 1 point if the variable HIV-AIDS equals to "Yes" ○ 2 points if the variable Any tumor (including lymphoma and leukemia) equals to "Yes" ○ 11 points if the variable Solid metastatic tumor equals to "Yes" ○ 1, 2, 3, 4, 5 or 6 points if the variable Age is greater or equal than 50, 60, 70, 80 90 or 100 years old, respectively
ACCI group	
Categorical variable (0, 1-2pts / 3-4pts / ≥ 5 pts)
 
Derived based on ACCI define above
 
Equals to:
 
"0" if ACCI is equal to 0 (the patient has no comorbidities)
 
"1-2pts" if ACCI is greater than 0 and less or equal to 2
 
"3-4pts" if ACCI is greater than 2 and less or equal to 4
 
≥ 5pts" if ACCI is greater or equal than 10

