9.7.4.2 Comparison of the incidence of stroke, major bleeding, death

Analyses will be performed independently for each event of interest stroke, major bleeding and death.

Survival analysis will be performed to compare incidence rate (stroke, major bleeding or death) in AF incident patients exposed and unexposed to OAC therapy **excluding those with a reported outcomes of interest up to 30 days prior index date**, using a Cox regression model. The Cox regressions models will consider the first event of interest occurring in AF incident patients exposed and unexposed to OAC. OAC exposure will be considered as time-dependent variable and the models will be adjusted for covariates defined below. By applying the OAC exposure variable as a time dependent variable, estimates of Hazard Ratio will account for switches and discontinuations. Time-dependent exposure Cox proportional hazards models will be used to estimate:

- The Crude hazard ratio (i.e. the incidence rate ratio), and therefore the risk of each outcome at any point during the follow-up since index date
- The adjusted hazard ratio on potential confounders including patient:
 - Time-fixed confounders: sex, age (<80, 80-90, >90 years old), prescriber's specialty at initiation of OAC, having malnutrition (yes/no), risk of falls (yes/no), morbid obesity (yes/no), history of stroke (yes/no), history of major bleeding (yes/no), at least one visit to a nursing home (yes/no), history of dementia (yes/no), concomitant treatments (e.g. receiving at least one antiplatelet drugs (yes/no), other anticoagulant drugs (yes/no), etc. - cf. *Table XV for all confounders*)
 - Time-dependent confounders: AOC treatment exposure

In a first model, patient exposure will be modelled according to five categories: exposure to apixaban, dabigatran or rivaroxaban, exposure to VKA or unexposed patients. In a second model, exposure to DOACs will be integrated instead of exposure to apixaban, dabigatran or rivaroxaban. For both models, the reference for comparison will be VKA exposure.

Same models will be performed on AF incident patients with a high thromboembolic risk (if modified CHAD₂DS₂VASC score is ≥ 2 for males and ≥ 3 females). Patient exposure will be modelled according to three categories: exposure to DOAC (Apixaban, Dabigatran or Rivaroxaban), exposure to VKA or unexposed patients. The reference for comparison will also be VKA exposure.

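### The Cox models do not adjust for active cancer or, less seriously, coronary disease, although both are primary subgroups already derived at baseline; the banded comorbidity index is only a blurred proxy for cancer

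*SAP*

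**What the plan says.** The primary objective (SAP 8.1) names five subgroups, among them "Patients with CAD" and "Patients reported with active cancer"; SAP 9.2.3.4 repeats the latter as "NVAF patients having an active cancer". Table V (SAP 9.4.1) derives both as yes/no baseline variables from hospital stays or long-term disease status over the two years before index:

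- CAD: "Is hospitalized with any diagnosis (i.e., main, related or associated diagnosis) of coronary arterial disease", codes I21, I22, I24 and I25.
- Active cancer: "Is hospitalized with any discharge diagnosis (i.e., main, related or associated diagnosis) of active cancer", codes C00-C80, D00-D09, D37-D48, Z51.0 and Z51.1.

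Three places say what the Cox models adjust for:

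- **SAP 9.7.4.2** lists sex, age band, prescriber specialty, malnutrition, falls risk, morbid obesity, "history of stroke (yes/no), history of major bleeding (yes/no), at least one visit to a nursing home (yes/no), history of dementia (yes/no", and concomitant treatments. It points to Table XV for the complete set.
- **Table XV** adds frailty, HAS-BLED, CHA2DS2-VASc (six bands) and ACCI (0, 1-2, 3-4, ≥5). It has no separate rows for prior stroke, major bleeding or dementia.
- **Footnotes to Tables A10 and A11** follow 9.7.4.2 but leave out prescriber specialty, frailty and all three scores.

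None of the three contains active cancer or CAD.

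**The concern.** The other three primary subgroup factors (age, prior stroke, frailty) each appear in at least one adjustment list; these two appear in none. If cancer or CAD is distributed differently between unexposed, VKA and DOAC person-time and also affects the outcome, the adjusted hazard ratios carry that difference. The SAP itself links CAD to bleeding: "The risk is also increased in patients with coronary arterial disease (CAD) due to antithrombotic therapy with dual antiplatelet and OAC".

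The cohort is large. At a constant 225,747 new users a year (SAP 9.5), 2016-2019 gives 225,747 × 4 = 902,988 exposed patients. Intervals should therefore be narrow, and a bias of a few percent could be read as a finding. None of the five sensitivity analyses in SAP 9.7.6 changes the covariates, and the limitations in SAP 9.9 do not mention confounding. The protocol (3.7.2.2) allows IPTW if necessary but names no covariates for it.

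**Working it through.** The plan states no power, margin or expected hazard ratio for this comparison, so there is no figure to reproduce. Three checks apply.

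**1. Does banded ACCI stand in for cancer?** Weights are from Table VI: age 1 to 6 points at 50, 60, 70, 80, 90 and 100; chronic pulmonary disease 1; heart failure 2; any tumour 2; and "11 points if the variable Solid metastatic tumor equals to" yes. Score = age points + comorbidity points.

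| Age | None | Pulmonary (+1) | Heart failure (+2) | Tumour (+2) | Metastatic (+11) |
|---|---|---|---|---|---|
| 65 | 2 | 3 | 4 | 4 | 13 |
| 75 | 3 | 4 | 5 | 5 | 14 |
| 80-89 | 4 | 5 | 6 | 6 | 15 |
| 90-99 | 5 | 6 | 7 | 7 | 16 |

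Reading the top band as labelled (≥5):

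- At 75, tumour is separated from no comorbidity but not from heart failure.
- At 80-89, the band says only that some scored comorbidity is present.
- From 90, everyone is in the top band and it says nothing about cancer.

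Table VI, however, defines the band labelled ≥5 as a score of at least 10. Read literally, scores 5-9 belong to no band. That includes every patient aged 70 or over with a non-metastatic tumour and no other scored condition (70: 3 + 2 = 5; 100: 6 + 2 = 8).

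**2. What stands in for CAD?** ACCI gives myocardial infarction 0 points and scores no other coronary item. The CHA2DS2-VASc vascular point uses I21, I22, I25.2 and I25.5 (hospital) or I21-I23 (long-term disease), plus peripheral disease. I24 and the rest of I25, which are in the Table V CAD variable, are not counted. The score is also capped at ≥5: a woman aged 75 or over with hypertension and heart failure already has 2 + 1 + 1 + 1 = 5, so a vascular point does not change her band. Antiplatelet and nitrate use in the four months before index (Table XIV) are covariates in all the lists.

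**3. How large could the cancer bias be?** A simulated Cox model used n = 60,000, a true exposure hazard ratio of 1.00, fixed exposure, mean age 75, two years of follow-up, and only cancer linked to exposure. Assumed inputs: cancer prevalence about 15% (a fifth metastatic), odds ratio between cancer and being unexposed 1.25 to 2.0, and cancer hazard ratio for death 1.5 to 3. Every model included age band and dementia. Estimated hazard ratios, unexposed versus exposed:

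| Cancer HR | Odds ratio | No ACCI | ACCI bands | Bands + cancer |
|---|---|---|---|---|
| 1.5 | 1.25 | 1.017 | 1.006 | 1.003 |
| 1.5 | 2.0 | 1.039 | 1.011 | 1.000 |
| 2 | 1.5 | 1.043 | 1.024 | 1.001 |
| 3 | 1.25 | 1.034 | 1.021 | 0.997 |
| 3 | 2.0 | 1.113 | 1.076 | 0.994 |

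Over all nine scenarios run, the range was about 1.02-1.11 without ACCI (as in the A10 footnote), 1.01-1.08 with the bands as labelled (as in Table XV), and 0.99-1.00 with active cancer added. On the log scale the bands removed 29% to 75% of the bias, and least when the cancer effect was strongest.

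A closed-form check on the last row uses the single-confounder factor [1 + p1(HR − 1)] / [1 + p0(HR − 1)]. With simulated prevalences p1 = 0.211 and p0 = 0.116 and HR = 3, it is 1.422 / 1.232 = 1.15. This is the same order as the unadjusted 1.11.

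**The case against.** The strongest reply is that much of this is already covered. Antiplatelet use is an explicit covariate, and antithrombotic therapy is the very route by which the SAP says CAD raises bleeding risk. Nitrates are adjusted for. Under Table XV, HAS-BLED scores aspirin and clopidogrel, and CHA2DS2-VASc scores infarction and peripheral disease. Frailty, malnutrition and nursing-home stay will also absorb some of the cancer effect. Table A8 will show cancer and CAD by exposure group, and Table A2 gives event rates by exposure within each subgroup, so an imbalance would be visible. Finally, being a descriptive subgroup does not make a variable a confounder, and no passage says that cancer influences whether or which OAC is given.

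Most of this stands for CAD, which is the weaker half: the proxy is incomplete but real. For cancer it stands only in part, because the proxies are coarse and the A10/A11 footnotes drop the scores and frailty. Displaying an imbalance does not adjust a hazard ratio. That cancer acts as a confounder remains a plausible assumption, not something the documents establish.

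A reader might go further and apply the single-confounder formula to larger contrasts. Prevalences of 25% versus 15% with a cancer hazard ratio of 3.5 give 1.625 / 1.375 = 1.18; 30% versus 12% give 1.75 / 1.30 = 1.35. Those figures treat cancer as wholly unadjusted and rest on prevalences found nowhere in the documents.

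**Conclusion.** The omission is confirmed in 9.7.4.2, Table XV and both table footnotes. Banded ACCI is a partial, blurred proxy for cancer that weakens from about age 75-80 and carries nothing from age 90. It carries nothing for CAD, which other covariates partly cover. Residual confounding of the adjusted hazard ratios is plausible, but neither its size nor its direction can be derived from the documents. The 1.01-1.08 (bands) and 1.02-1.11 (no ACCI) ranges illustrate cancer and death, unexposed versus exposed, under assumed prevalences and effects.

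Three further inferences are not supported:

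- **That the bias would dominate the confidence interval.** The documents give no interval width.
- **That bias in bleeding, or in DOAC versus VKA, has been shown.** Neither was calculated, and no magnitude was worked out for CAD.
- **That the problem falls on an elderly majority.** The documents put two-thirds of AF patients at 75 or over, but at 75 the bands still separate cancer from no comorbidity; the collapse into any scored comorbidity begins at 80.

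The change is worth making because it costs almost nothing and can only narrow the gap. The omission does not invalidate the analysis.

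**What to change.** 1. Add active cancer, solid metastatic tumour and history of CAD as separate time-fixed yes/no covariates in 9.7.4.2, Table XV and the A10/A11 footnotes.
2. Make those lists agree. State in each whether prescriber specialty, frailty, HAS-BLED, CHA2DS2-VASc, ACCI, prior stroke, major bleeding and dementia are in the model.
3. Correct the ACCI top band in Table VI to a score of 5 or more, matching its own label, Table XV and the table shells.
4. Before using active cancer, reconcile its look-back: six months in the SAP abstract and protocol Table A1.5, two years in Table V. Add the haematological codes C81-C97, which Table V leaves out and the Table VI any-tumour variable largely covers (C81-C85, C88, C90-C97).

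The cost is three extra model terms from variables the SAP already derives, one corrected threshold and one extended code list. With about 0.9 million exposed patients the degrees of freedom are negligible, and no new data are needed.

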3.7.2 Outcomes of secondary objectives

3.7.2.1 To describe the characteristics of non-valvular AF patients exposed and unexposed to OAC and to compare the incidence rate of stroke, major bleeding, and death between those two populations

In cross-sectional analyses and every year, we will describe for AF subpopulations, sociodemographic characteristics, comorbidities, medical history of interest and associated treatments defined in Table A1.

The modified CHAD2DS2VASC score for thromboembolic risk and HAS-BLED (19) for hemorrhagic risk will be estimated every year during the study period using adapted algorithms to SNDS.

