9.4.2 *Derived Variables for the Primary Objective*

The incidence rate for each event of interest (stroke, major bleeding and death) in AF incidents patients between 2016 and 2019 will be derived by treatment exposure sequence and by unexposed sequence, for overall and by sub-populations (see section 9.2.3.4).

First the treatment exposure sequences will be derived (Table VII). A patient could have several lines i.e., one line by patient by treatment sequence.

Table VII. Derived variables for identification of treatment exposure or unexposed sequences

Variable	Definition
Start date of treatment sequence	
Date variable
 
Equals to the date of the first delivery of each specific treatment (VKA, Apixaban, Rivaroxaban or Dabigatran) of the sequence
 
ATC codes: B01AA, B01AF02, B01AF01, B01AE07 (respectively)

End date of treatment sequence	
Date variable
 
The end date of treatment sequence is defined as:
 
 – The day before the date of first delivery of another OAC if the patient switches to another OAC 
OR

	
 – Date of the last delivery of treatment sequence supplemented by 30 days (treatment duration), at the condition that there is no other OAC reimbursement in the next 60 days 
ATC codes: B01AA, B01AF02, B01AF01, B01AE07
 
For sensitivity analyses: duration of 30 days and 90 days of maximal number of days allowed for being refilled will be considered.

Treatment sequence	
Category variable (VKA / Apixaban / Rivaroxaban / Dabigatran)
 
Equals to “VKA / Apixaban / Rivaroxaban / Dabigatran” if the patient has a reimbursement of VKA, Apixaban, Rivaroxaban or Dabigatran during the treatment sequence
 
ATC codes: B01AA, B01AF02, B01AF01, B01AE07(respectively)

Start date of unexposed sequence	
Date variable
 
The start date of unexposed sequence is defined as:
 
 – The index date for AF patients without an OAC reimbursement in 30 days after the index date (for sensitivity analyses, the inclusion date will be the index date for all incident patients, whether or not patients received OAC therapy within 30 days of the inclusion date) 
OR
 
 – The day after the End date of treatment sequence if the patient has stopped an OAC (at the condition that there is no other OAC reimbursement in the next 60 days, period defined as “the grace period”)

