9.4.3.2 Comparison of the incidence of stroke, major bleeding, death

The incidence rate ratio for each event of interest (stroke, major bleeding and death; see [Table VIII](#) for derivation of events of interest) will be compared using a Cox regression model with OAC exposure (see [Table VII](#) for derivation of exposure sequences) considered as time-dependent variable adjusted for covariates. Covariates will be derived at index date as indicated in [Table XV](#).

Table XV. Derived variables for confounders

Variable	Definition
Age	Categorical variable (<80 years old / 80–90 / >90 years old) See Table III
Sex	Binary variable (Female / Male) See Table III
Prescriber's specialty at initiation of OAC	Categorical variable (Hospital-based physician/ City cardiologist/ Generalist practitioners/Other) See Table III
Having Malnutrition	Binary variable (Yes / No) See Table III
Risk of falls	Binary variable (Yes / No) See Table III
Frail patients	Binary variable (Yes / No) See Table V
Morbid obesity	Binary variable (Yes / No) See Table VI
At least one visit to a nursing home	Binary variable (Yes / No) See Table VI
Concomitant treatments	Binary variable (Yes / No) for each concomitant treatment listed in Table XIV

For example, for antiplatelet drugs, equals to “Yes” if the patient has at least one reimbursement for an antiplatelet drug in the 4 months before the index date
	
HAS-BLED score	Categorical variable (0, 1, 2, 3, ≥ 4) See Table VI
CHAD₂DS₂VASC score	Categorical variable (0, 1, 2, 3, 4, ≥ 5) See Table VI
Age adjusted Charlson Cormordity Index (ACCI) adapted to SNDS data	Categorical variable (0, 1-2, 3-4, ≥ 5) See Table VI XII

9.4.3.3 *Estimation of the AF annual standardized incidence rate and prevalence*

All the variables in [Table XVI](#) will be derived for all AF patients in France in 2016, 2017, 2018 and 2019.

Table XVI. Derived variables for incidence and prevalence

Variable	Definition
Incident AF patient	Binary variable (Yes / No) See Table X
Prevalent AF patient	Binary variable (Yes / No) Equals to “Yes” if the patient is diagnosed AF during the historical period Patients belonging to the study population

9.4.3.4 *To describe the use of oral anticoagulants (OACs) in AF patients initiating treatment (AF patients exposed to OAC therapy)*

Table XVII. Derived variables for OAC treatment pattern

Variable	Definition

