- with integration of all incident AF patient (i.e. inclusion of patients with an event of interest between inclusion date and index date)

Table A11. Risk of stroke, major bleeding or death in AF incident patients with a high thromboembolic risk (modified CHA2DS2VASC score is ≥ 2 for males and ≥ 3 females)

	Event		Crude risk ¹		Adjusted risk ^{2,*}	
	n	%	HR	[95%CI]	HR	[95%CI]
Risk of stroke						
Exposure to DOACs	xx	(x.x)	x.xx	[x.xx–x.xx]	x.xx	[x.xx–x.xx]
Exposure to Apixaban						
Exposure to Dabigatran						
Exposure to Rivaroxaban						
Unexposed to OAC**	xx	(x.x)	x.xx	[x.xx–x.xx]	x.xx	[x.xx–x.xx]
Exposure to VKA	xx	(x.x)	ref		ref	
Risk of major bleeding						
Exposure to DOACs	xx	(x.x)	x.xx	[x.xx–x.xx]	x.xx	[x.xx–x.xx]
Exposure to Apixaban						
Exposure to Dabigatran						
Exposure to Rivaroxaban						
Unexposed to OAC**	xx	(x.x)	x.xx	[x.xx–x.xx]	x.xx	[x.xx–x.xx]
Exposure to VKA	xx	(x.x)	ref		ref	
Risk of death						
Exposure to DOACs	xx	(x.x)	x.xx	[x.xx–x.xx]	x.xx	[x.xx–x.xx]
Exposure to Apixaban						
Exposure to Dabigatran						
Exposure to Rivaroxaban						
Unexposed to OAC**	xx	(x.x)	x.xx	[x.xx–x.xx]	x.xx	[x.xx–x.xx]
Exposure to VKA	xx	(x.x)	ref		ref	

AF : Non Valvular Atrial Fibrillation; HR: hazard ratio; 95%CI: 95% confidence interval; DOAC= Direct oral anticoagulant; VKA= Antivitamin K;
 Note: For considering DOAC treatment in models, two regressions models will be performed for this table: one model with "Exposure to DOACs" as independent variable; second model with exposure for each molecule within the class of DOAC (Apixaban, Dabigatran, Rivaroxaban).

¹From a time-dependant exposure Cox proportional hazards model

²From a time-dependant exposure to OAC and time-fixed covariates Cox proportional hazards model;

*Adjusted on the following covariates at or from index date: age (<80, 80-90, >90 years old), sex, having malnutrition, risk of falls, morbid obesity, history of stroke, history of major bleeding, at least one visit to a nursing home, history of dementia, each concomitant treatments

**Unexposed to OAC correspond to the period where the patients are not exposed to OAC.

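### The Cox models in SAP 9.7.4.2 update OAC exposure over time but hold nearly all confounders at index, leaving the hazard ratios (chiefly unexposed versus OAC, for death) open to time-varying confounding

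*SAP*

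**What the plan says.** For objective 3, SAP 9.7.4.2 states: "OAC exposure will be considered as time-dependent variable and the models will be adjusted for covariates defined below". Confounders are then listed under two labels. The time-fixed list holds sex, age, prescriber's specialty, malnutrition, falls risk, obesity, history of stroke, major bleeding and dementia, nursing-home visit and concomitant drugs, and refers to Table XV for the rest (CHA2DS2-VASc, HAS-BLED, ACCI, frailty). The time-dependent list has one entry: "Time-dependent confounders: AOC treatment exposure".

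SAP 9.4.3.2 sets the timing: "Covariates will be derived at index date as indicated in" Table XV. The one exception is prescriber's specialty, which is dated at OAC initiation and so has no value for patients who never start. The notes to Tables A10 and A11 call the covariates time-fixed, but another A11 note reads "Adjusted on the following covariates at or from index date", which does not fit.

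The section also claims: "By applying the OAC exposure variable as a time dependent variable, estimates of Hazard Ratio will account for switches and discontinuations". Under Table VII, unexposed time after stopping begins on "The day after the End date of treatment sequence if the patient has stopped an OAC", whatever the reason for stopping.

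**The concern.** Consider a patient who has a major bleed on treatment and then stops. In the death model that patient's later time counts as unexposed, but with the pre-bleed HAS-BLED, ACCI and bleeding history. Follow-up is not cut at the bleed: SAP 9.2.1.4 ends it only at death, study end or last reimbursement, and each event has its own model. The excess risk after the bleed is then credited to being off OAC.

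The mechanism fits the SAP's own account. Its background says that bleeding risk calls for regular review of treatment, and Table XII defines contraindications to OAC. Time-dependent exposure puts the person-time in the right exposure category; it does not make the reallocated time comparable.

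At stake is the reading of the unexposed rows in Tables A10 and A11. Lack of data on unexposed patients is the study's stated rationale (SAP 7.2), and Protocol 2.4 foresees use of the results in regulatory submissions.

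**Working it through.** **1. Does any other part of the plan deal with this?**

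- Aalen fallback (9.7.4.2): changes the hazard scale; no updated confounders.
- Sensitivity analyses (9.7.6): change the start date, calendar period, case definition, grace period, or allocation of grace-period events; none changes covariate timing.
- Limitations (9.9): silent.
- Protocol 3.7.2.2: allows inverse-probability weighting if needed, not described as time-varying; the SAP does not carry it forward.
- Protocol 3.7.2.1: the two risk scores "will be estimated every year during the study period using adapted algorithms to SNDS". This is descriptive work, but it shows that updating is feasible.

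**2. Size figure.** The plan gives no power, event count or significance level for the Cox models. Its only size figure is the number exposed. From 225,747 new users a year: × 4 = 902,988 (2016–2019); × 5 = 1,128,735. Neither the SAP's 1.3 million nor the Protocol's 1 million is reproduced exactly. That is a separate matter; about 0.9 million is used below.

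**3. Form of the bias.** Suppose a health change multiplies the hazard by k, and a share p1 of unexposed and p0 of exposed person-time falls after it. With no OAC effect, the spurious ratio is roughly

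HR ≈ [1 + p1(k − 1)] / [1 + p0(k − 1)].

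It equals 1 if k = 1 (no effect on outcome) or p1 = p0 (no link with stopping or switching). Both links are needed.

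**4. Simulation with true OAC hazard ratio 1.** Monthly Cox partial likelihood, VKA as reference, one baseline risk factor. Assumed, not from the documents: start 25% VKA, 55% DOAC, 20% unexposed; base hazard 5% a year; health change 10–20% a year; stopping 10%, VKA-to-DOAC switching 3% and restarting 10% a year; staggered entry over 4 years. The percentages and counts are runs whose 95% CI excluded 1.

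| Health change multiplies hazard / stop-switch rate | n (runs) | Unexposed vs VKA, index-only | DOAC vs VKA, index-only | Unexposed vs VKA, health updated |
|---|---|---|---|---|
| ×3 / ×1 (control) | 10,000 (600) | 1.001; 6.3% | 1.003; 7.8% | 1.001; 6.7% |
| ×1 / ×4 (control) | 10,000 (600) | 0.998; 5.7% | 1.000; 4.5% | 0.998; 5.8% |
| ×1.5 / ×2 | 10,000 (600) | 1.015; 6.3% | 0.999; 5.0% | 0.999; 5.0% |
| ×1.5 / ×2 | 100,000 (100) | 1.016; 10% | 0.996; 1% | 0.999; 4% |
| ×1.5 / ×2 | 900,000 (16) | 1.017; 6 of 16 | 0.999; 1 of 16 | 1.000; 0 of 16 |
| ×2 / ×4 | 10,000 (600) | 1.074; 13.7% | 1.006; 5.7% | 0.994; 5.0% |
| ×3 / ×4 | 10,000 (600) | 1.142; 39.0% | 1.020; 5.2% | 1.004; 5.2% |
| ×3 / ×4 | 100,000 (100) | 1.137; 100% | 1.015; 10% | 1.000; 8% |
| ×3 / ×4 | 900,000 (16) | 1.137; 16 of 16 | 1.012; 6 of 16 | 1.000; 2 of 16 |
| ×3 / ×8 | 10,000 (600) | 1.255; 83.8% | 1.017; 4.7% | 0.996; 3.7% |

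With only switching tied to health (×3 / ×4, n = 900,000), DOAC versus VKA was 1.019, with 10 of 16 intervals excluding 1. Time-varying stabilised weights gave 0.995–1.001 (two scenarios, three runs each, n = 900,000). Monte Carlo error around 5% is 1.96 × √(0.05 × 0.95/600) ≈ 2 points at 600 runs and about 4 at 100; the 16-run results are coarse.

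**5. Is updating at the start of each exposure sequence enough?** A patient who declines but stays on one drug starts no new sequence under Table VII and keeps the old profile. A second simulation pooled the exposed. Its assumptions were 75% treated at index, health event 10% a year, stopping 25% a year, base death 5% a year, restarting 0–25% a year and follow-up uniform over 0–4 years (n = 100,000, 12 runs per setting).

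| Event multiplies death / stopping | Index-only | Updated at sequence start | Updated continuously |
|---|---|---|---|
| ×2 / ×2 | 1.04–1.05 | 1.01 | 1.01 |
| ×3 / ×3 | 1.10–1.11 | 1.02–1.03 | 1.00 |
| ×4 / ×4 | 1.19–1.21 | 1.05–1.07 | 0.99–1.01 |

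Updating at sequence start removes most of the bias but not all; in the last row 67–100% of its intervals still excluded 1.

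**The case against.** Several points limit the concern, and they stand.

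- A reader might infer that the plan's test will falsely reject a null of no OAC effect. The SAP states no null, level or test for the Cox models, only hazard ratios with 95% CIs; its two-sided 5% level belongs to the cost comparisons. The most that can be said is that a CI may exclude 1.
- A reader might also infer that every hazard ratio in Tables A10 and A11 is biased. The models take the first event, so stopping after a first bleed cannot bias the bleeding model, nor stopping after a first stroke the stroke model. DOAC versus VKA moved by no more than about 2% in the simulations.
- The yearly scores in Protocol 3.7.2.1 serve description, so Protocol and SAP do not conflict on this.
- Updating has a price. A bleed or stroke after index can be a consequence of OAC use, and HAS-BLED and CHA2DS2-VASc include such histories. Conditioning on them can remove part of a real OAC effect. The simulations had no OAC effect, so they cannot show how much.

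None of this answers the central point: health changes after index cannot enter the model, and the SAP does not say so.

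**Conclusion.** The design gap is confirmed by the text and nothing else in the plan closes it. The adjusted hazard ratios are confounded if health changes after index drive both the outcome and stopping or switching. This matters most for unexposed versus OAC, and most for death.

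The size depends on assumed strengths: about 1.015 in the mild case and 1.25 in the strong case for unexposed versus VKA when OAC has no effect, and no distortion if either link is absent. In the mild case, frequent exclusion of 1 reflects the very large cohort rather than a large bias. The claim about switches and discontinuations holds for exposure classification only.

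Objective 3 is secondary and the primary analysis is descriptive, so this is a should-fix: a cheap improvement to what objective 3 can support.

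**What to change.** 1. In SAP 9.7.4.2, 9.7.6 and Tables A10/A11, pre-specify a second analysis reported beside the index-only model. Update CHA2DS2-VASc, HAS-BLED, ACCI, prior stroke, prior major bleeding, frailty and concomitant treatments, with the existing look-back rules, at fixed intervals (for example quarterly) or at event dates, not only at sequence start. Add active cancer, which is not a separate Table XV covariate.
2. Preferably also run it as a Cox model with time-varying stabilised inverse-probability weights (a marginal structural model), because some updated covariates can be consequences of OAC.
3. Limit the sentence on switches and discontinuations to exposure classification.
4. List residual time-varying confounding in 9.9.
5. Reconcile the A11 note on covariate timing with its time-fixed label.

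Cost: SAP text, repeated derivation of variables already defined, and programming; no new data. The covariate-updated model may adjust away part of an OAC effect, which is why the index-only model is kept beside it.
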